7.1.7. Data Adjustments/Handling/Conventions

Adverse events will be coded using the MedDRA version 24.0 thesaurus.

A treatment related AE is any AE with a relationship to the study drug as judged by the investigator.

For partial start dates:

- If the year is unknown, then do not impute the date but instead assign a missing value.
- If the year is known, but the month or month and day is unknown, then:
 - If the year matches the year of first dose date and the end date (if present) is after first dose date, or the AE/medication is ongoing, then impute as the month and day of the first dose date. If this produces a date after the end date, assign 01 January.
 - Otherwise, assign 01 January.
- If the year and month are known, but the day is unknown, then:
 - If the month and year match the month and year of the first dose date, then impute as the day of the first dose date. If this produces a date after the AE/medication end date, assign 01.
 - Otherwise, assign 01.

For partial end dates:

- If the year is unknown, then do not impute the date but assign as missing value.
- If the year is known but the month or month and day is unknown, then:
 - If the year matches the year of the last date of the study (date of last contact if subject lost to follow-up; date of completion or early termination otherwise), then impute as the month and day of the last date of the study.
 - Otherwise, assign 31 December.
- If the year and month are known, but day is unknown, then:
 - If the month and year match the month and year of the last date of the study, then impute as the day of the last date of the study.
 - Otherwise, assign the last day of the month.

These conventions will be applied only to adverse events.

Missing times will be not be imputed, they will be left as missing.

8. Study Patients/Subjects and Demographics

8.1. Disposition of Patients/Subjects

Subject disposition information will be listed. Disposition for all subjects will include tabulations of the number of subjects enrolled, completing, and withdrawing, along with reasons for withdrawal, for each cohort (and overall).

8.2. Protocol Violations and Deviations

Protocol deviations will be listed.

8.3. Demographics and Other Baseline Characteristics

Summary statistics for age, sex, ethnicity, race, height, weight, and BMI will be summarized by cohorts for subjects in the Safety population. For the continuous variables, the number of non-missing values and the mean, standard deviation, minimum, median, and maximum will be tabulated. For the categorical variables, the counts and proportions of each value will be tabulated.

Demographic and anthropometric variables (age, sex, ethnicity, race, height, weight, and BMI) will be listed by subject. In addition, medical history, smoking history, and vaccination history will be listed by subject.

8.4. Exposure and Compliance

IP exposure and dosing information will be listed for each subject.

8.5. DTH Responses

The DTH responses will be listed for each subject by visit.

9. Safety Analysis

Tables for the safety analyses will be conducted on the Safety population, which includes any subjects in Cohort 1, 2, or 3 who receive at least 1 intradermal injection of the IPs. Listings will include enrolled subjects.

For this study, AESIs are anaphylactic reactions and enhanced disease from repeated exposure to SAR-CoV-2 (in subjects who have recovered from SARS-CoV-2 infection or in subjects recently vaccinated against SARS-CoV-2).

9.1. Adverse Events

Treatment emergent AEs are defined as AEs that either commenced following initiation of study treatment or was present prior to study treatment but increased in frequency or severity following initiation of study treatment. Adverse events of special interest (AESI) include anaphylactic reaction and enhanced disease from repeated exposure to SARS-CoV-2 (in subjects who have recovered from SARS-CoV-2 infection or in subjects recently vaccinated against SARS-CoV-2).

All AEs occurring after completion of the informed consent process and before the end of study, regardless of relationship to study drug, will be included and classified by system organ class (SOC) and preferred term (PT) using the Medical Dictionary for Regulatory Activities (MedDRA) v24.0.

For treatment-emergent AEs (TEAEs), the following will be summarized and presented for the Safety population:

An overall summary of TEAEs, which includes:

- a. the number and percentage of patients experiencing a TEAE
- b. the number and percentage of patients experiencing a TEAE by strongest relationship to IP
- c. the number and percentage of patients experiencing a TEAE by highest severity grade
- d. the number and percentage of patients experiencing a systemic allergic reaction by highest grade according to the World Allergy Organization Grading Scale for Systemic Allergy Reactions
- e. the number and percentage of patients experiencing a treatment emergent SAE (TESAE)
- f. the number and percentage of patients experiencing a TEAE leading to study discontinuation
- g. the number and percentage of patients experiencing a treatment emergent AE of Special Interest

In the overall summary of TEAEs table, besides tabulating the number and percentage of patients, the total number of TEAE episodes will also be provided. If a patient has repeated episodes of a particular TEAE, all episodes will be counted in the summary table.

All occurrences of all AEs will be listed for each patient. The listing will contain the following information: verbatim term, SOC, PT, severity (Grade 1 = Mild, Grade 2 = Moderate, Grade 3 = Severe, and Grade 4 = Potentially Life Threatening), World Allergy Organization Grading Scale for Systemic Allergic Reactions (Grades 1-5) [where applicable], relationship to study medication, date/time and day of onset, date/time and day of resolution, the outcome, whether the event was life-threatening, fatal, or a TEAE, SAE, or AESI, if it requires or prolongs hospitalization, persistent or significant disability/incapacity, congenital anomaly or birth defect,

or important medical event. Listings will be sorted by patient identification number, onset date, SOC, and PT. If the onset date is completely missing, these events will be presented first. If the onset date is missing a month or a day, these events will be presented before any complete dates. AEs with a relationship to study drug or possibly related will be considered related.

Local skin reaction AEs will be listed by 7-point Likert scales indicating severity of the events:

- 1 = No problem;
- 2 = Minimal problem (can be easily ignored without effort);
- 3 = Mild problem (can be ignored with effort);
- 4 = Moderate problem (cannot be ignored but does not influence my daily activities);
- 5 = Moderately severe problem (cannot be ignored and occasionally limits my daily activities);
- 6 = Severe problem (cannot be ignored and often limits my concentration on daily activities);
- 7 = Very severe problem (cannot be ignored and markedly limits my daily activities and often requires rest).

All collected data will be presented in listings.

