#### **12.1.5. Vital Signs**

Vital signs (systolic and diastolic blood pressure, pulse, respiratory rate and body temperature) will be measured at Visit 1 prior to skin test administration. Vitals will also be collected after Stage 1 and Stage 2 skin test administrations, 30 minutes post-administration of IPs and controls.

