#### **13.5.1. Adverse Events**

All AEs will be listed. The number and percent of subjects experiencing an event will be tabulated for each System Organ Class and Preferred Term. The AEs will also be tabulated according to severity and causality.

For this study, AESIs are anaphylactic reactions and enhanced disease from repeated exposure to SARS-CoV-2 (in subjects who have recovered from SARS-CoV-2 infection or in subjects recently vaccinated against SARS-CoV-2).

Serious AEs (SAE) will be listed separately.

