#### **13.5.2. Clinical Laboratory Tests**

Individual data listings of laboratory results will be presented for each subject. Flags will be attached to values outside of the laboratory's reference limits along with the Investigator's assessment. Clinically significant laboratory test abnormalities that were considered AEs by the Investigator will be presented in the AE listings.

Clinical laboratory tests (observed values) will be summarized descriptively in tabular format. Shift tables will be presented for select laboratory parameters.

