#### **13.5.3. Vital Signs**

Individual data listings of vital signs (observed and change from baseline) will be presented for each subject. Individual clinically significant vital signs findings that were considered AEs by the Investigator will be presented in the AE listings.

Observed values as well as change from baseline data will be summarized descriptively in tabular format.

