9.2. Clinical Laboratory Evaluations

Individual data listings of laboratory results will be presented for each subject. Flags will be attached to the value outside of the laboratory's reference limits.

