9.3. Vital Signs

Individual data listings of vital signs (observed and change from baseline) will be presented for each subject.

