9.6. Concomitant Medication

Prior and concomitant medications will be listed. Medications that started before initial intradermal injections of investigational products will be considered prior medications whether or not they were stopped before initial intradermal injections of investigational products. Any

medications continuing or starting after initial intradermal injections of investigational products will be considered to be concomitant. If a medication starts before initial intradermal injections of investigational products and continues after, it will be considered both prior and concomitant.

Medications will be coded using World Organization Drug Dictionary Anatomical Therapeutic Chemical classes and preferred terms.

10. Changes from Planned Analysis

Because the outcome of area of induration for the DTH reactions was not as anticipated, the DTH reactions will not be statistically analyzed. Any primary, secondary, or exploratory efficacy endpoint will be omitted from the analysis and only safety will be assessed.

11. Other Planned Analysis

Not applicable for this study.

12. References

ASA. (2018) Ethical Guidelines for Statistical Practice. Prepared by the Committee on Professional Ethics, April 2018. <http://www.amstat.org/about/ethicalguidelines.cfm>

ICH (1998). ICH Harmonised Tripartite Guideline. Statistical Principles for Clinical Trials E9; 1998. https://database.ich.org/sites/default/files/E9_Guideline.pdf

RSS. (2014) The Royal Statistical Society: Code of Conduct, 2014. <https://rss.org.uk/about/policy-and-guidelines/code-of-conduct/>.

ELECTRONIC RECORD AND SIGNATURE DISCLOSURE

From time to time, [REDACTED] (we, us or Company) may be required by law to provide to you certain written notices or disclosures. Described below are the terms and conditions for providing to you such notices and disclosures electronically through the DocuSign system. Please read the information below carefully and thoroughly, and if you can access this information electronically to your satisfaction and agree to this Electronic Record and Signature Disclosure (ERSD), please confirm your agreement by selecting the check-box next to 'I agree to use electronic records and signatures' before clicking 'CONTINUE' within the DocuSign system.

Electronic Signature Responsibilities

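### Safety is the only analysis left, yet the SAP omits safety tables the protocol requires, does not declare it, and defines TEAE in two conflicting ways

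*SAP*

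**What the plan says.** Protocol 13.5 sets out the safety displays.

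- **Adverse events (13.5.1):** "The number and percent of subjects experiencing an event will be tabulated for each System Organ Class and Preferred Term". Tables by severity and causality are also required.
- **Laboratory tests (13.5.2):** a descriptive table of observed values, and "Shift tables will be presented for select laboratory parameters".
- **Vital signs (13.5.3):** "Observed values as well as change from baseline data will be summarized descriptively in tabular format".

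The SAP provides the following.

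- **Adverse events (9.1):** "For treatment-emergent AEs (TEAEs), the following will be summarized and presented for the Safety population". The display named is one overall summary. It covers any TEAE, strongest relationship, highest severity, systemic allergic reaction by grade, serious TEAEs, TEAEs leading to discontinuation, and AESIs.
- **Laboratory tests (9.2):** "Individual data listings of laboratory results will be presented for each subject", with flags for out-of-range values.
- **Vital signs (9.3):** "Individual data listings of vital signs (observed and change from baseline) will be presented for each subject".

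The SAP states its changes from plan in sections 2.3 and 10, in the same words: "Any primary, secondary, or exploratory efficacy endpoint will be omitted from the analysis and only safety will be assessed". No safety change is mentioned in either place.

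The SAP has two TEAE definitions. Section 7.1.6 requires onset after the first injection of investigational product. Section 9.1, like protocol 14.1, also counts an event already present that becomes more frequent or more severe after treatment starts. Section 7.1.7 can impute a partial onset date to the first-dose date, but it leaves missing times missing.

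**The concern.** With efficacy removed, the safety tables are the study's only planned aggregate results. The overall TEAE summary counts subjects by severity, causality and seriousness, but it identifies only two kinds of event by type: systemic allergic reactions and AESIs. Local-reaction Likert scores are also listed only. No specified table would therefore separate injection-site events from, say, headache or fatigue.

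Vital signs taken 30 minutes after each stage are the only scheduled quantitative systemic readings after injection. Their change from baseline would not be summarised.

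The TEAE flag drives most of the one AE table that remains, so a programmer needs a single definition. As written, an event that began before the first injection and worsened afterwards is not a TEAE under 7.1.6 and is one under 9.1. An injection-day event with no recorded time, or with an imputed date, has no defined status.

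**Working it through.** This is mainly a comparison of planned outputs. The documents contain no figure to reproduce; protocol synopsis and SAP 3.2 both say that no formal sample-size calculation was done.

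**Step 1. Protocol tables against the SAP**

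| Protocol requirement | SAP provision | Declared in SAP 2.3 or 10? |
|---|---|---|
| AE n (%) by SOC and PT (13.5.1) | Not among items a to g; SOC and PT appear only as coding (9.1) and as listing columns | No |
| AEs by severity and causality (13.5.1) | Kept at subject level in the overall summary | Not needed |
| Laboratory descriptive summary (13.5.2) | Listing only (9.2) | No |
| Laboratory shift tables (13.5.2) | Absent (9.2) | No |
| Vital signs, observed and change from baseline (13.5.3) | Listing only (9.3) | No |

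The SAP's general text on by-visit denominators (4.1), scheduled visits in summaries (7.1.5) and the change-from-baseline formula (7.1.6) does not commit to any of the missing tables.

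**Step 2. Which omissions cost information**

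- *Laboratory.* Protocol Table 3 schedules these tests at Visit 1 only, and protocol 12.2.2 draws blood before injection. A shift table would have no scheduled post-baseline value. Declaring the change is enough.
- *Vital signs.* Protocol 12.1.5 says "Vitals will also be collected after Stage 1 and Stage 2 skin test administrations, 30 minutes post-administration of IPs and controls", in addition to a reading before administration. Change from baseline can therefore be computed at two scheduled times.
 - Sets: 90 planned subjects x 2 = 180, if all subjects complete both stages.
 - Readings: 180 x 5 parameters (systolic and diastolic pressure, pulse, temperature, respiratory rate) = 900. The synopsis text for Stage 1 omits respiratory rate; four parameters throughout would give 180 x 4 = 720.
- *AEs by SOC and PT.* The coded data exist, so the table needs only programming.

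**Step 3. TEAE definitions**

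| Event | SAP 7.1.6 | SAP 9.1 and protocol 14.1 |
|---|---|---|
| New onset after first injection | TEAE | TEAE |
| Onset before first injection, worse afterwards | Not a TEAE | TEAE |
| Injection-day onset, time missing or date imputed | Undefined: depends on how after is programmed | Undefined |

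**Step 4. Size of the TEAE effect**

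For each affected subject with no other TEAE, the any-TEAE percentage moves by 1/n:

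- cohort of 30: 1/30 = 3.3 points
- all 90 subjects: 1/90 = 1.1 points

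A subject who has another TEAE moves it by 0. These figures assume the planned numbers. Enrolment is approximate, and if a cohort had 25 subjects (my assumption) the shift would be 1/25 = 4.0 points.

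**The case against.** The strongest reply is that nothing is lost from the record. All AEs are listed with SOC, PT, severity and relationship, and with about 90 subjects the counts could be rebuilt by hand. Vital-sign abnormalities that the investigator judges to be AEs reach the AE listings under protocol 13.5.3. Those with onset after injection then enter the TEAE counts. The laboratory omission is close to empty because testing is scheduled only at Visit 1. The TEAE conflict should touch few events: consent is given on Day 1 or at most two days earlier, and if a worsened condition is recorded with the date of worsening as its onset, both definitions count it. Missing times should also be uncommon for reactions seen during the observed 60 and 30 minutes. Finally, the documents show only a difference between protocol and SAP; they do not show when or why the tables were left out.

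Most of this stands as a limit on weight. The data remain available, the laboratory point is one of documentation, and the number of affected TEAEs is probably small. The count of vital-sign readings measures volume and says nothing about bias.

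It does not answer the main point. Listings are not the tables the protocol promised. Counting only the vital-sign changes judged to be AEs leaves out any shift below that judgement. SAP 9.1 does mention classification by SOC and PT, but that sentence describes coding, and the only TEAE display it goes on to name is the overall summary. A definition that conflicts within one SAP has to be settled however few events it affects.

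**Conclusion.** The concern holds. Followed as written, the SAP would report safety without AE incidence by type and without any summary of post-injection vital signs, both of which the protocol requires. The laboratory summary and shift tables are absent as well, and none of this is declared. The two TEAE definitions cannot both be applied.

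The size is moderate. Up to 180 vital-sign sets go unsummarised, assuming 90 subjects who all complete both stages. The any-TEAE rate moves by at most 3.3 points per affected subject in a cohort of 30, or 1.1 points overall. How many subjects would be affected cannot be known from the documents. Data integrity is not threatened. This should be corrected before the safety tables are produced.

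**What to change.** 1. **SAP 9.1:** add a table of TEAEs, n (%) of subjects by SOC and PT, by cohort and overall.
2. **SAP 9.3:** restore the descriptive summary of observed vital signs and change from baseline at 30 minutes after Stage 1 and after Stage 2.
3. **SAP 7.1.6:** replace the TEAE definition with that of protocol 14.1, already used in SAP 9.1. Add that an onset on the injection date with a missing or imputed time counts as treatment-emergent unless it is recorded as starting before the first injection of investigational product.
4. **SAP 10:** list every remaining departure from protocol 13.5, including the dropped laboratory summary and shift tables, and give the Visit 1-only schedule as the reason.

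The cost is SAP wording and two standard tables to program from data already collected. TEAE counts may be slightly higher under the wider definition.

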#### **14.2.2 Severity of Adverse Event**

The severity of an AE refers to the extent of clinical abnormalities and to the extent of which an AE affects the subject's daily activities ([Table 8](#), FDA Guidance for Industry; Toxicity Grading Scale for Healthy Adult and Adolescent Volunteers Enrolled in Preventive Vaccine Clinical Trials, 2007). The term "severity" is used to describe the intensity of an event. This is not the same as "serious". Seriousness, not severity, serves as the guide for defining regulatory reporting

obligations. The highest severity grade attained should be reported, for AEs with divergent severities.

Severity will be categorized according to event category (local, systemic, other).

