#### **14.2.4 Local Adverse Event by 7-point Likert Scale**

The subject self-reported severity of local AEs will be graded by the subject using a 7-point Likert scale. The scale will assess the subjects' evaluation of severity of erythema (redness), pain, pruritis and swelling following the intradermal injection.

Full details can be found in [Appendix 3](#).

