Illness or clinical adverse event (as defined according to applicable regulations)	No interference with activity	Some interference with activity not requiring medical intervention	Prevents daily activity and requires medical intervention	ER visit or hospitalization

Local AEs will be graded as described in [Section 14.2.4](#). Adverse events of systemic allergic reaction will be graded according to the World Allergy Organization Grading Scale for Systemic Allergic Reactions (see [Appendix 1](#)).

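### Safety is the only analysis left, but the SAP departs from the protocol's safety tables without declaring it and gives local reactions no summary of their own

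*SAP*

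**What the plan says.** SAP 2.3 and Section 10 remove all primary, secondary and exploratory efficacy endpoints and leave safety as the only assessment. Section 10 lists no other change.

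For adverse events, SAP 9.1 states that they "will be included and classified by system organ class (SOC) and preferred term (PT"), and then specifies one overall summary of treatment-emergent events (TEAEs) with items a to g. Two of these items matter here:

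- item b: "the number and percentage of patients experiencing a TEAE by strongest relationship to IP"
- item c: "the number and percentage of patients experiencing a TEAE by highest severity grade"

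For local reactions, which SAP 2.2.2 and Protocol 7.2.1 name as a safety endpoint, SAP 9.1 says "Local skin reaction AEs will be listed by 7-point Likert scales indicating severity of the events". It closes with "All collected data will be presented in listings". SAP 9.2 and 9.3 give listings for laboratory tests and vital signs.

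Protocol 13.5 plans more: adverse events tabulated by system organ class and preferred term and also by severity and causality (13.5.1), a descriptive laboratory table with shift tables for selected tests (13.5.2), and a descriptive table of observed and change-from-baseline vital signs (13.5.3).

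On grading, Protocol 14.2.2 says "Severity will be categorized according to event category (local, systemic, other"). Protocol 14.2.4 says "The subject self-reported severity of local AEs will be graded by the subject using a 7-point Likert scale". The text under Table 8 says "Local AEs will be graded as described in" that section.

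**The concern.** When safety is all that remains, the section headed as changes from the planned analysis should let a reader trust that the rest of the safety plan stands. Here it does not. Anyone reading SAP Section 10 alone would conclude that the safety reporting in Protocol 13.5 is intact.

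A second difficulty is interpretation. Each subject receives eight injections, two of which are controls, and one of those controls is chosen because it should react. A single per-subject TEAE count cannot say whether a local reaction came from a peptide product, from the diluent or from CANDIN. In a study described as dose-finding, local tolerability of the products is a natural question, and the planned summary does not address it.

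**Working it through.** **Step 1. The two plans side by side.**

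| Output | Protocol | SAP | Status in SAP Section 10 |
|---|---|---|---|
| Vital signs | 13.5.3: table of observed values and changes | 9.3: listing of both | Change not declared |
| Laboratory | 13.5.2: descriptive table; shift tables for selected tests | 9.2: listing with out-of-range flags | Change not declared |
| Adverse events by organ class and preferred term | 13.5.1: counts and percentages | 9.1: events coded, no such table specified | Change not declared |
| Adverse events by severity and causality | 13.5.1: tabulated | 9.1: items b and c | Kept in the overall summary |
| Likert scores for local reactions | No table promised in 13.5, although an endpoint in 7.2.1 | 9.1: listing | Not a departure |

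**Step 2. What the changed tables would have held.**

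- Vital signs. Protocol 12.1.5 and footnote h of Table 3 give five measures: systolic pressure, diastolic pressure, pulse, temperature and respiratory rate. They are taken before injection, 30 minutes after Stage 1 and 30 minutes after Stage 2. Change summaries: 5 measures × 2 post-injection times = 10 in the protocol, 0 in the SAP. (The synopsis text for Stage 1 omits respiratory rate; on that reading Stage 1 has four measures.)
- Laboratory. Tests are scheduled only at Visit 1 (Table 3, footnote l), with blood drawn before injection (12.2.2). SAP 7.1.5 tabulates scheduled visits only. A shift table would therefore have 0 scheduled post-baseline values, so its removal costs little and only needs declaring.

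**Step 3. How a control-site reaction reaches the TEAE count.**

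1. Protocol Table 4: diluent is injection 1, the three 1:10 products are injections 2 to 4, CANDIN is injection 5, and the three undiluted products are injections 6 to 8. Controls are 2 of 8 sites.
2. SAP 7.1.6 counts as treatment-emergent any event starting after the first product injection, which is injection 2. A CANDIN reaction always starts after that.
3. Protocol 12.1.11 has observed site changes recorded as adverse events, and 12.1.10 expects CANDIN to give a positive result. Against this, 14.1 describes an adverse event as untoward and unintended, so whether sites recorded expected CANDIN reactions is not known from the documents.
4. If recorded, the reaction counts in item a. Item b separates it only in part: the item refers to the investigational product, and Protocol 10.3 says CANDIN is not one, but Protocol 14.2.3 has the investigator rate relationship to study drug without saying whether that covers CANDIN.
5. Of items a to g, 0 of 7 split by site, product, strength, or local against systemic.

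**Step 4. How far mixing could move the count (illustration on assumed rates).** Let c be the proportion of subjects with a control-site reaction recorded as an adverse event, and r the proportion with a product-site reaction so recorded; assume independence. The unseparated local rate is 1 − (1 − c)(1 − r), and the excess over r is c(1 − r).

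| c | r = 0: unseparated rate | r = 30%: unseparated rate | Excess at r = 30% |
|---|---|---|---|
| 0% | 0% | 30% | 0 points |
| 10% | 10% | 37% | 7 points |
| 50% | 50% | 65% | 35 points |
| 90% | 90% | 93% | 63 points |

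The documents give neither c nor r. If sites did not record expected control reactions, c is near zero and the distortion disappears.

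**Step 5. The severity scale in item c.** The SAP 9.1 listing gives each adverse event a grade from 1 to 4, and lists the Likert score from 1 to 7 separately. Protocol 14.2.4 and the text under Table 8 send local events to the Likert scale. The two scales do not line up: a 3 is severe on the first and a mild problem on the second. The SAP does not say in words which one feeds item c for a local event.

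**The case against.** The strongest reply is that nothing is lost. All collected data are listed; clinically significant vital-sign findings judged to be adverse events go to the adverse-event listings and, if treatment-emergent, enter the summary; severity and causality are tabulated; and SAP 8.5 lists the induration responses by subject and visit. Coding by organ class and preferred term could be read as implying a table. The protocol never promised a local-reaction table by site, and Appendix 3 words the Likert question without naming a site, so such a table may not be possible.

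Much of this stands, and it rules out several stronger readings that a reader might infer:

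- That local reactions appear nowhere but in listings. Those recorded as adverse events do enter items a to c; what is missing is a summary of their own.
- That a by-site table was planned and dropped. It was not; it would be an improvement.
- That item c has no workable scale. The natural reading of SAP 9.1 is a grade of 1 to 4 for every event, with the Likert score listed in addition. One clarifying sentence would settle it.
- That CANDIN reactions certainly inflate the TEAE count. This depends on site recording practice, which the documents leave open.
- That the missing laboratory shift tables hide post-injection findings. None were scheduled.

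What the reply does not answer is that two planned sets of tables became listings, a third table is not specified, and the section meant to declare changes mentions none of it. Listings of about 90 subjects are no substitute for a summary when the summary is the whole analysis.

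**Conclusion.** The point holds as a gap in reporting and interpretability. The vital-sign and laboratory departures are plain on the text; the organ-class table is less explicit, since the SAP's wording is open to either reading. Vital signs (10 change summaries reduced to 0) and the organ-class table matter most, because both would carry post-injection information. The laboratory change is a matter of declaration only. The separation of control-site reactions is worth having because none of the seven summary items provides it, but its practical effect runs from nil upwards with an unknown recording rate.

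The documents do not support a claim that safety data are lost or that a safety signal is concealed. The conclusion assumes that the protocol supplied is the version the SAP cites (v2.0, amendment 01), which cannot be confirmed because its title pages were removed, and that no case report form settles the site question.

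**What to change.** 1. Restore the descriptive vital-sign table: five measures at baseline, with observed value and change 30 minutes after each stage, by cohort and overall. SAP 9.3 already derives the changes for its listing. Specify the adverse-event table by organ class and preferred term.
2. Declare the removal of the laboratory tables in SAP Section 10, giving as the reason that tests are scheduled only at Visit 1.
3. Where injection site was recorded, show TEAEs with control-site-only reactions (CANDIN or diluent) separated from the rest. State whether study drug in the causality rating includes CANDIN, and how sites recorded expected control reactions. Tabulate Likert scores by cohort, and by site if recorded, descriptively and without tests; for by-site rows use subjects who received that injection as the denominator, because Stage 2 is conditional on Stage 1. If site was not recorded for adverse events or Likert scores, say so as a limitation.
4. Add one sentence stating that item c uses the investigator's grade of 1 to 4 and that the Likert score is reported separately, if that is what was done.

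The cost is a few descriptive tables and a fuller Section 10. Items 1 and 2 need only planned data, and item 4 needs only confirmation of what was done. Item 3 needs a clarification from the sponsor and depends on whether site was recorded.
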